Potential confounders that could affect the pancreatic juice PGE₂ concentration include concomitant use of aspirin or additional NSAIDs during the study. We have attempted to mitigate this possibility by excluding persons who habitually use aspirin or NSAIDs, and we will advise study participants to limit their use of these drugs to occasional prn use, when absolutely needed. Participants may nevertheless use occasional aspirin or NSAIDs, and this will be captured in the study drug diaries. Participant use of these drugs will be characterized using descriptive statistics, and if appropriate included in study analyses. Other potential confounders include occurrence of acute pancreatitis. Participants who are hospitalized with acute pancreatitis between baseline and completion of day 28 will be withdrawn from the study, and not considered accrued. Milder fluctuations in underlying pancreatic inflammation may or may not be symptomatic, and we cannot directly control this source of variation, but the blinded and randomized allocation of study subjects should minimize the impact of this confounder on study results. We doubt that administration of either steroids or oral pancreatic enzyme supplements would decrease PJ PGE₂ levels, but this can also be assessed using study data if sufficient numbers of subjects use these medications.

Pharmacologically the study design assesses the effect of steady-state (rather than single-dose) IN dosing on PJ PGE₂ concentrations. A single-dose study design would permit a pharmacokinetic analysis including time to peak physiologic effect after a single dose of study medication, and this

data might impact decisions regarding drug dosage and frequency of administration. However such a study would be difficult to perform, because PJ cannot be repeatedly assayed at various time points after single dose drug administration in the same subject, hence requiring construction of composite time curves utilizing multiple subjects to assess the single-dose pharmacokinetics of each drug and dose assessed. In addition the results of a single-dose study would be less relevant to subsequent therapeutic trials than the steady-state study design proposed here.

Subject accrual may be hindered by the need to return to the study center for a repeat endoscopic exam done for research purposes. However given the size of the clinical pancreatitis practices at Mayo Clinic and Ohio State University, complete study accrual within 2 years should be readily accomplished. We anticipate that reimbursement of study participants for completion of the study protocol will improve compliance with study interventions and accrual of complete study data.

4.2 SCIENTIFIC RATIONALE FOR STUDY DESIGN

The study rationale is presented in the Introduction section of this protocol. A placebo control group was chosen to adequately control for changes in PJ PGE₂ that might occur over time due to other clinical and disease factors. A physiologic primary endpoint is being studied and the study is powered to identify superiority of IN over placebo.

4.3 JUSTIFICATION FOR DOSE

There is no published data on the effect of IN on human pancreatic COX-2 activity. Usual clinical doses of oral indomethacin are 25-50 mg BID to TID. This study's dose of oral IN was chosen based on standard clinical dosing, published literature showing that similar blood levels are achieved with oral vs rectal administration, and the fact that steady-state administration of IN 50 mg BID orally should result in higher blood and tissue drug levels than 100 mg administered rectally once. Common side effects of IN such as dyspepsia are often dose related. Five doses of drug are required to achieve pharmacological steady state.

4.4 END OF STUDY DEFINITION

A participant is considered to have completed the study if he or she has completed all phases of the study including the last visit or the last scheduled procedure shown in the Schedule of Activities (SoA), Section 1.3.

The end of the study is defined as completion of the last visit or procedure shown in the SoA in the trial globally.

5 STUDY POPULATION

5.1 INCLUSION CRITERIA

1. Any gender, age \geq 18 years and \leq 700 years

2. Diagnosed with chronic pancreatitis per American Pancreatic Association guidelines (pancreatic calcifications and/or Cambridge 3-4 changes on CT, MRI, and/or ERCP)
3. Scheduled for an upper GI endoscopic procedure (EGD or EUS) for clinical or research indications (not conflicting with current investigation).
4. Able to provide written informed consent.
5. Serum creatinine within normal laboratory range, as measured within 30 days of the baseline study endoscopy.
6. For females of reproductive potential: willing to use highly effective contraception while taking study medication and for an additional 5 days after completing study medication.

5.2 EXCLUSION CRITERIA

1. Diagnosed with acute pancreatitis requiring hospitalization within the 6 weeks prior to study enrollment.
2. Habitual use of aspirin or non-steroidal anti-inflammatory medications (NSAIDs), defined as use more than once per week.
3. Any use of aspirin or NSAIDs within 1 week of baseline study endoscopy procedure.
4. Allergy to secretin, indomethacin or NSAIDs.
5. History of known chronic renal insufficiency or cirrhosis.
6. History of coronary artery disease, angina pectoris, myocardial infarction, cerebrovascular accident (stroke), or transient ischemic accident (TIA).
7. History of peptic ulcer or gastrointestinal bleeding.
8. Incarcerated.
9. Found to have active GI ulceration at the time of baseline endoscopy.
10. Hospitalized for acute pancreatitis while participating in this research protocol.
Participants who are hospitalized for an episode of acute pancreatitis during study participation will be withdrawn from the study, and considered non-accrued.
11. Patients with indwelling pancreatic duct stents.
12. Patients status post Whipple procedures or Roux-en-Y gastric bypass due to inability to collect pancreatic fluid via the natural ampulla, unless having an EDGE procedure for clinical reasons.

5.3 LIFESTYLE CONSIDERATIONS

During this study, participants are asked to avoid taking aspirin or NSAIDs. Participants will be given a list of NSAID generic and brand names for their reference.

5.4 SCREEN FAILURES

Screen failures are defined as participants who consent to participate in the clinical trial but from whom baseline pancreas juice specimens are not obtained and study drug is never dispensed. A minimal set of screen failure information is required to ensure transparent reporting of screen

failure participants, to meet the Consolidated Standards of Reporting Trials (CONSORT) publishing requirements and to respond to queries from regulatory authorities. Minimal information includes demography, screen failure details, eligibility criteria, and any serious adverse event (SAE).

Individuals who do not meet the criteria for participation in this trial (screen failure) because of a modifiable factor may be rescreened. Rescreened participants should be assigned the same participant number as for the initial screening.

5.5 STRATEGIES FOR RECRUITMENT AND RETENTION

Target study sample size is 32 participants who complete all aspects of the study protocol. Up to 300 potential participants may be screened to achieve target enrollment. Participants will be recruited from the clinical gastroenterology and endoscopy practices at Mayo Clinic Rochester and Ohio State University.

Potential participants may be approached in person or by telephone. Participants will be recruited without regard to race, ethnicity or gender. Vulnerable populations (children, incarcerated persons, persons unable to provide informed consent) are excluded from participation.

Participants who complete the study protocol, including 28 days of study medication and follow-up endoscopy with pancreas juice collection, will be paid \$250 remuneration, and up to an additional \$250 reimbursement for travel expenses including mileage, parking, hotel and airfare. In order to receive reimbursement, you must provide a copy of the original receipts for those expenses.

Participants who complete the first pancreatic juice collection but who do not complete the entire protocol will receive \$50 remuneration and no additional reimbursement. Participants who do not complete the first pancreatic juice collection will not receive remuneration or reimbursement.

6 STUDY INTERVENTION

6.1 STUDY INTERVENTION(S) ADMINISTRATION

6.1.1 STUDY INTERVENTION DESCRIPTION

The study intervention is oral indomethacin or identical placebo. Indomethacin is an FDA approved, commonly prescribed NSAID. Commercially available indomethacin will be utilized in this study and over-encapsulated to match the placebo capsules. A package insert for indomethacin is attached to this protocol.

6.1.2 DOSING AND ADMINISTRATION

Participants in both study arms will receive study medication, one capsule orally BID for 28 days. Those in the indomethacin arm will receive indomethacin 50 mg BID, and those in the placebo arm will receive placebo capsules BID.

Participants will be advised not to make up missed doses. They will be advised to take a dose of study medication on the morning of their follow-up endoscopy, 2 hours prior to their scheduled procedure time, with a sip of water. At the time of follow-up endoscopy they will return any unused study medication.

6.2 PREPARATION/HANDLING/STORAGE/ACCOUNTABILITY

6.2.1 ACQUISITION AND ACCOUNTABILITY

Indomethacin capsules are purchased by Mayo Clinic Research Pharmacy. Mayo Clinic Production Lab overencapsulates indomethacin capsules and creates matching lactose placebo capsules in bulk supply. After preparation, blinded medication is returned to Research Pharmacy and stored at 20-25C.

Research Pharmacy utilizes an electronic inventory management system (Vestigo) to maintain investigational drug inventory and prescription dispensing records.

Investigator issues an electronic prescription for study medication and sends to Research Pharmacy. The prescription is processed, patient is randomized by pharmacy staff, and a blinded pharmacy label is generated and attached to the study medication bottle. Study medication prescriptions are picked up by study team at Research Pharmacy, or mailed to patient's home address upon request.

Unused study medication is returned to Research Pharmacy where capsules are counted, return count is recorded in Vestigo, and capsules are destroyed per policy. Expired medications are removed from inventory and destroyed per policy.

Investigator may prescribe up to 31 days of study medication, so that in case of rescheduling of the Day 28 endoscopy the subject may continue to take study medication for up to an additional 3 days.

6.2.2 FORMULATION, APPEARANCE, PACKAGING, AND LABELING

Generic indomethacin 50 mg capsules are obtained from Cardinal Health by Research Pharmacy. Research pharmacy sends indomethacin bottles to Production Lab where they are encapsulated and matching placebo capsules are created. Blinded batches are labeled and returned to Research Pharmacy for storage until dispensation. When a prescription is received, pharmacy staff randomizes patient and places ordered quantity of study medication into a prescription bottle. Bottle is labeled in a blinded fashion, and dispensed to study team for dispersal to patient.

6.2.3 PRODUCT STORAGE AND STABILITY

Indomethacin and placebo capsules are stored in Research Pharmacy at room temperature (20-25C). Daily min/max temperatures are recorded manually every business day, and electronic temperature data is captured continuously via TempTrak. Temperature data is available for viewing upon request.

6.2.4 PREPARATION

Described above.

6.3 MEASURES TO MINIMIZE BIAS: RANDOMIZATION AND BLINDING

Randomization: Subjects will be assigned to receive IN or placebo according to a computer generated randomization list composed of randomized blocks of sizes of 2 or 4. Two separate sets of blocks will be created, one for subjects with alcoholic CP and the other for those with other causes of CP. Within each block, equal number of subjects will be assigned to IN and placebo. Separate sets of blocks will be provided for Mayo and Ohio State. The randomization lists will be computer generated by the study statistician ([name]), and kept in a secure computer file and paper study binder in the Mayo and Ohio State Research Pharmacies. No investigators or study personnel other than [name] and staff at Mayo/OSU research pharmacies will have knowledge of the randomization list. [name] will not participate in any aspect of subject recruitment, subject allocation, conduct of the study, or data ascertainment, but will perform data analysis with de-identified data.

Subject allocation will be known only to the staff of the Mayo and Ohio State Research Pharmacies, who will assign subjects to IN or placebo according to their randomization list provided by [name]. Allocation will be performed by matching the subject's study number with the randomization list. Allocation will not be revealed to subjects, investigators, other study personnel, or clinicians caring for subjects until all subjects have completed the clinical trial or for medical emergency. Because subjects, investigators, and study personnel will be blinded, they will not be able to determine subject allocation before or during data ascertainment.

Allocation will be performed on the day of the participant's baseline endoscopy with pancreas juice collection. One container of study medication containing 28 days of medication (56 capsules) will be dispensed to the participant that day.

In case a subject is allocated to receive study medication, but is withdrawn from the study before completing the protocol, study medication will be returned to the Research Pharmacy for disposal.

Blinding: Study medication will be labelled "indomethacin 50 mg or placebo capsule" with the subject's name, hospital or clinic number, study IRB number, and subject number. Placebo and IN capsules will be identical in appearance. The investigators, study coordinator, and clinical caregivers will remain blinded to subject allocation throughout the data ascertainment and data entry phase of the study.

The success of blinding will be evaluated by asking the investigator, the study coordinator, and the subject the following question during each telephone follow-up visit: "Which treatment group is this subject/were you assigned to: placebo, active drug, or unsure?"

6.4 STUDY INTERVENTION COMPLIANCE

Participants will complete a daily symptom and medication diary. Unused study drug will be returned by the participant on the day of their follow-up endoscopy procedure. Unused capsules will be counted, documented and returned to the research pharmacy for disposal. Indomethacin levels will be measured in blood collected on the morning of the follow-up endoscopy procedure.

6.5 CONCOMITANT THERAPY

Participants who have taken aspirin or NSAIDs at any time during the 7 days prior to their baseline endoscopy procedure are excluded from participation. Participants will be asked to refrain from taking aspirin or NSAIDs throughout the 28 days of study drug administration.

6.5.1 RESCUE MEDICINE

Not applicable.

7 STUDY INTERVENTION DISCONTINUATION AND PARTICIPANT DISCONTINUATION/WITHDRAWAL

7.1 DISCONTINUATION OF STUDY INTERVENTION

Study interventions (endoscopy, pancreas juice collection, dispensing of study medication) will be halted if there are 2 or more SAEs attributable to study interventions, pending IRB review. If study interventions are halted, participants who are actively taking study medication may continue to take study medication and complete the study protocol, but no new study medication will be dispensed.

7.2 PARTICIPANT DISCONTINUATION/WITHDRAWAL FROM THE STUDY

Participants are free to withdraw from participation at any time upon request. An investigator may withdraw a participant from the study for the following reasons:

1. Found to have active gastrointestinal ulceration at the time of their baseline, clinically indicated GI endoscopy procedure.
2. Positive pregnancy test in a woman of child bearing potential.
3. Significant study medication non-compliance (defined as failure to take at least 66% of study medication doses, as determined during telephone follow-up calls).
4. Hospitalized for acute pancreatitis during study participation.
5. Other acute illness that requires breaking study blinding and discontinuing study medication for clinical reasons.

7.3 LOST TO FOLLOW-UP

A participant will be considered lost to follow-up if he or she fails to complete more than one telephone follow-up visit within 48 hours of its scheduled time, or fails to return or reschedule study visit 3.

The following actions must be taken if a participant fails to return to the clinic or is not available by telephone for a required study visit:

- The site will attempt to contact the participant and reschedule the missed visit within 24 hours, and counsel the participant on the importance of maintaining the assigned visit schedule and ascertain if the participant wishes to and/or should continue in the study.
- Before a participant is deemed lost to follow-up, the investigator or designee will make every effort to regain contact with the participant (where possible, 3 telephone calls and, if necessary,

- a certified letter to the participant's last known mailing address or local equivalent methods). These contact attempts will be documented in the participant's medical record or study file.
- Should the participant continue to be unreachable, he or she will be considered to have withdrawn from the study with a primary reason of lost to follow-up.

8 STUDY ASSESSMENTS AND PROCEDURES

8.1 EFFICACY ASSESSMENTS

The *endoscopic pancreatic function test (ePFT)* will be performed at baseline and on day 28. ePFT is a standardized test used in medical pancreatology clinical practice that involves administration of intravenous secretin (0.2 mcg/kg slowly over one minute) to stimulate pancreatic juice secretion, followed by aspiration of pancreatic juice from the duodenum via an endoscope. Some subjects will undergo a baseline ePFT as part of their routine clinical care; other subjects, who are having upper GI endoscopy or endoscopic ultrasound (EUS) performed as part of their clinical care, will undergo ePFT for research purposes during their baseline, clinically indicated endoscopy. Fluid will be aspirated from the duodenum via an endoscope at baseline and from 0-10 and 10-20 minutes following secretin administration, and processed per CPDPC pancreas juice/fluid SOP. Participants will be instructed take their study drug with a sip of water 2 hours prior to their follow-up research endoscopy with ePFT on day 28.

PJ bicarbonate and lipase concentrations will be measured on duodenal aspirates from each time point using a previously validated method.¹⁸ *PGE2 concentrations* will be measured in saliva, blood, and pancreatic juice from baseline and day 28 using a tandem mass spectroscopy assay developed and validated at Mayo Clinic Rochester. *Peak IN drug levels* will be measured in blood on day 28, providing an assessment of participant compliance with study drug administration. Exploratory analysis of molecular analytes (cytokine and microbiome) in blood and saliva will be done to measure effect of IN administration.

The *Brief Pain Inventory (BPI)* and the *PROMIS-10* are validated scales that quantify pain and quality of life, respectively, and will be completed at baseline and day 28.

A *medication and pain diary* will be completed daily by all subjects at baseline and during the 28-day treatment period, including all narcotics and over-the-counter medications used. Oral opioid usage will be expressed in oral morphine equivalents for purposes of data analysis.

8.2 SAFETY AND OTHER ASSESSMENTS

Screening of potential participants for eligibility will be done during the screening visit. Additional elements (serum creatinine result, presence of active GI ulceration) will be determined subsequent to the screening visit when laboratory results are available, and during the baseline endoscopy.

Physical Examination, including chest, cardiac, and abdominal exams, will be documented in the patient's medical record within 30 days of their baseline endoscopy procedure.

Height and weight will be measured within 30 days of the participant's baseline endoscopy procedure.

Serum creatinine will be measured within 30 days of the participant's baseline endoscopy procedure. This test will be performed for research purposes, and the result placed in the patient's medical record, if it is not being performed clinically. Participants with serum creatinine outside of the laboratory normal range will be withdrawn from the study and considered non-accrued.

Blood draw will be up to 30 cc at study visit 1 (baseline) and up to 20 cc at study visit 3 (day 28). This includes up to 10 cc for measurement of serum PGE2 at both time points. Baseline blood draw also includes up to 10 cc for measurement of serum creatinine if not already measured for clinical purposes, and up to 10 cc for aspirin and NSAID screens. Day 28 blood draw also includes up to 10 cc for indomethacin level. Details of biospecimen handling are documented in the study biospecimen SOP.

Endoscopic procedures will be performed on clinical GI Endoscopy Units at the current standard of clinical care at Mayo Clinic Rochester and Ohio State University, including the use of monitored anesthesia care (MAC) or general anesthesia (GA) at the discretion of the attending gastroenterologist and anesthesiologist. Participants will receive pre-procedure evaluation, intra-procedural monitoring, and post-procedural recovery care identical to that provided to patients undergoing endoscopy in these units. Staff nurses, anesthetists, and GI endoscopists will be available to assess symptoms and adverse events and provide appropriate treatment during endoscopic procedures and their recovery period. Participants will be discharged from the endoscopy unit when they meet the unit's standard discharge criteria.

Secretin Administration: Secretin will be administered intravenously during GI endoscopy procedures at baseline and day 28 at a weight-based dose of 0.2 mcg/kg administered slowly over one minute. Fluid will be aspirated from the duodenum via an endoscope at baseline and from 0-10 and 10-20 minutes following secretin administration, and processed per CPDPC pancreas juice/fluid SOP. Participants will be instructed take their study drug 2 hours prior to their follow-up research endoscopy with ePFT on day 28. Details of biospecimen handling are documented in the study biospecimen SOP.

Medical History and Endoscopic Findings: Subjects with a history of cirrhosis, chronic renal insufficiency, gastroduodenal ulceration, GI bleeding, stroke, myocardial infarction, or hospitalization for acute pancreatitis within 6 weeks of enrollment are excluded from participation. Subjects found to have active gastric or duodenal ulceration at the time of baseline endoscopy are also excluded. Women who are pregnant or nursing and persons older than 70 years of age, who are at higher risk for aspirin or NSAID-related adverse events, are also excluded from this study.

Women of child bearing potential must have a negative serum or urine pregnancy test within 48 hours of initiating study drug treatment, and must agree to remain sexually abstinent or use birth control measures for the duration of their study participation and for 5 days afterward.

A woman is NOT considered to be of "child-bearing potential" if their menses ceased within the past 2 years or if they have undergone hysterectomy.

The following birth control methods are acceptable for study purposes:

- Hormonal methods, such as birth control pills, patches, injections, vaginal ring, or implants
- Barrier methods (such as a condom or diaphragm) used with a spermicide (a foam, cream, or gel that kills sperm)
- Intrauterine device (IUD)
- Abstinence (no sex)

Weekly Follow-up: Subjects will be contacted weekly by telephone by a study coordinator weekly during study drug administration, as well as several days following completion of study drug administration. The coordinator will ask about compliance with study medication, completion of the daily symptom and medication diary, and new or worsening symptoms or health concerns. Subjects will be encouraged to report new symptoms or health problems to study staff, which will result in communication between a physician-investigator and the subject. Subjects will be able to report symptoms or ask questions at other times by telephone. A study physician will be available to respond to subjects by telephone at all times.

Study enrollment logs containing individually identifiable private information will be stored in secure non-public sites at each study site, as detailed above.

Incidental findings noted during study endoscopy will be described in the clinical endoscopy report generated after each endoscopy exam, which is placed in the patient's medical record. Subjects will be informed of incidental findings and encouraged to follow-up with their clinical care professional about any incidental findings.

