1.2 SCHEMA

1.3 SCHEDULE OF ACTIVITIES (SOA)

Procedures	Screening Day -28 to 0	Study Visit 1 Day -28 to 0	Study Visit 2 Day 0	Phone Call A Day 7	Phone Call B Day 14	Phone Call C Day 21	Study Visit 3 Day 25 - 28	Phone Call D Day 56 - 58
Review inclusion/exclusion criteria	X							
Informed consent	X							
Demographics		X						
Medical history		X						
Medications (documented)		X					X	
BPI, PROMIS-10 completed		X					X	
List of NSAIDS to avoid given to participant		X						
Vital signs including height, weight		X						
Physical Exam documented		X						
Blood collection and processing, including serum creatinine if not already checked within 30 days		X					X	
Saliva collection and processing		X					X	
Pregnancy test ^a			X				X	
Randomization			X					
GI Endoscopy			X				X	
Pancreas juice collection and processing			X				X	
Dispense study medication			X					
Interim history form (telephone interview)				X	X	X		X
Daily medication and pain diary				X-----X				
Collect unused study medication and document							X	
Complete Case Report Forms (CRFs)	X	X	X	X	X	X	X	X

^a Urine pregnancy test within 48 hours prior to GI endoscopy, in women of childbearing potential.

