Indomethacin (IN) is a nonsteroidal anti-inflammatory drug (NSAID), and many drugs in this class are available over-the-counter. IN was chosen for use in this protocol because rectally administered IN is known to have a beneficial anti-inflammatory effect in human pancreas for prevention of post-ERCP pancreatitis. Like other NSAIDs, IN has a low risk of complications, including allergic reactions, gastrointestinal ulceration, GI bleeding, and a small increased risk of vascular events such as stroke or myocardial infarction. Patients with a history of allergy to NSAIDS, current or past gastroduodenal ulceration, or past history of stroke, myocardial infarction, or coronary artery disease are excluded from participation in this study.

Alternative approaches and treatments: The study protocol utilizes the least invasive, least risky method of assessing human pancreatic COX-2 activity at baseline and after drug treatment.

There are no effective medical therapies for CP that alter the natural history of the disease. Study participants will be patients with CP who will be receiving concurrent care for their condition as clinically appropriate and as determined by their treating physician.

Women who are pregnant or nursing: Risks of endoscopy and sedation may be increased in women who are pregnant or nursing, and they are excluded from participation in this study.

Women of child-bearing potential will undergo a urine pregnancy test within 48 hours of their research EGD exam. In addition, at the time of enrollment (as detailed in the ICF) they must agree to one of the following birth control methods:

- Hormonal methods, such as birth control pills, patches, injections, vaginal ring, or implants
- Barrier methods (such as a condom or diaphragm) used with a spermicide (a foam, cream, or gel that kills sperm)
- Intrauterine device (IUD)
- Abstinence (no sex)

They must use birth control for the entire study and for at least 5 days after their last dose of study drug.

Psychological, legal and financial risks: Study questionnaires will collect confidential information, including medical history, medications used, pain ratings, and quality of life information. Public release of this information might have adverse consequences for study participants. All study data will therefore be stored in secure paper files or de-identified, password-protected electronic databases.

Protections Against Risk

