Endoscopic procedures will be performed on clinical GI Endoscopy Units at the current standard of clinical care at Mayo Clinic Rochester and Ohio State University, including the use of monitored anesthesia care (MAC) or general anesthesia (GA) at the discretion of the attending gastroenterologist and anesthesiologist. Participants will receive pre-procedure evaluation, intra-procedural monitoring, and post-procedural recovery care identical to that provided to patients undergoing endoscopy in these units. Staff nurses, anesthetists, and GI endoscopists will be available to assess symptoms and adverse events and provide appropriate treatment during endoscopic procedures and their recovery period. Participants will be discharged from the endoscopy unit when they meet the unit's standard discharge criteria.

Subjects with a history of gastroduodenal ulceration, GI bleeding, stroke, myocardial infarction, or currently active acute pancreatitis are excluded from participation. Subjects found to have active gastric or duodenal ulceration at the time of baseline endoscopy are also excluded. Women who are pregnant or nursing and persons older than 70 years of age, who are at higher risk for aspirin or NSAID-related adverse events, are also excluded from this study.

Women of child-bearing potential (i.e., women who are pre-menopausal and have not had a hysterectomy) must have a negative urine pregnancy test within 48 hours of initiating study drug treatment, and must agree to remain sexually abstinent or use birth control measures (as detailed above) for the duration of their study participation and for 5 days afterward.

Subjects will be contacted weekly by telephone by a study coordinator during their 4 weeks of study drug administration. The coordinator will ask about compliance with study medication, completion of the daily symptom and medication diary, and new or worsening symptoms or

health concerns. Subjects will be encouraged to report new symptoms or health problems to study staff, which will result in communication between a physician-investigator and the subject. Subjects will be able to report symptoms or ask questions at other times by telephone. A study physician will be available to respond to subjects by telephone at all times.

Study enrollment logs containing individually identifiable private information will be stored in secure non-public sites at each study site, as detailed above.

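### Section 8.2 words the child-bearing exemption backwards and conflicts with section 2.4 on who must have a pregnancy test

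*Combined protocol and SAP*

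**What the plan says.** Two sections define the term, and they differ.

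- Section 8.2 lists who is not of child-bearing potential: a woman qualifies "if their menses ceased within the past 2 years or if they have undergone hysterectomy".
- Section 2.4, under Protections Against Risk, defines who is: "women who are pre-menopausal and have not had a hysterectomy". The same sentence requires these women to have a negative urine pregnancy test within 48 hours of starting study drug.

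The pregnancy tests depend on this term:

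- Schedule of Activities (1.3), footnote a, for the tests at Visit 2 (Day 0) and Visit 3 (Day 25 to 28): "Urine pregnancy test within 48 hours prior to GI endoscopy, in women of childbearing potential".
- Section 2.4, on the research endoscopy: "Women of child-bearing potential will undergo a urine pregnancy test within 48 hours of their research EGD exam".
- Section 8.2, on starting drug: "Women of child bearing potential must have a negative serum or urine pregnancy test within 48 hours of initiating study drug treatment".

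Contraception is also required by inclusion criterion 6 in section 5.1, under a different term that is not defined there: "For females of reproductive potential: willing to use highly effective contraception while taking study medication".

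**The concern.** An interval in a rule of this kind is there to require sustained cessation before a woman is treated as unable to conceive. The 8.2 sentence does the opposite. A woman whose periods stopped a few weeks or months ago fits its words, and missed periods are one way an unrecognised pregnancy presents.

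The timing makes this matter. Section 6.3 states: "Allocation will be performed on the day of the participant's baseline endoscopy with pancreas juice collection". Drug is dispensed the same day, so the Visit 2 test is the one the schedule places before treatment. The Visit 3 test precedes the follow-up endoscopy. The protocol states the hazard itself: "Risks of endoscopy and sedation may be increased in women who are pregnant or nursing". Two sites, or two coordinators at one site, could handle the same woman differently, each following a section of the protocol.

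**Working it through.** The plan gives no figure to reproduce and no arithmetic applies. The check sets the two definitions side by side for five illustrative women and then follows the consequence through the test schedule.

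| Woman | Of child-bearing potential under 2.4? | Under 8.2 as worded |
|---|---|---|
| 1. Menstruating regularly, no hysterectomy | Yes | Not exempted |
| 2. Pre-menopausal, no hysterectomy, menses stopped two months ago | Yes | Exempted |
| 3. 18 months past menopause, no hysterectomy | No | Exempted |
| 4. 10 years past menopause, no hysterectomy | No | Not mentioned |
| 5. After hysterectomy | No | Exempted |

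**Where they conflict.** Only woman 2 is classified in opposite ways, and the 8.2 answer is the unsafe one. Woman 4 is a gap: 8.2 says a woman is exempt if a condition holds, not only if it holds, so it is silent about her and 2.4 exempts her. That gap is harmless, but it shows that the sentence is a slip, since a rule on cessation of menses should cover the woman who is furthest past it. The profiles were chosen to show the logic, so one in five is not a rate in the trial population.

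**Tests for woman 2.** Under 2.4 she has the pre-drug test by that section's own definition, and the test before the research endoscopy. That matches the two in the schedule, Visits 2 and 3. If 8.2 alone supplies the meaning of the term in footnote a, neither applies. The count is two under one section and none under the other.

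**If the start of drug is delayed.** Section 4.1 allows up to 4 weeks between baseline specimens and the first day of drug. The 48-hour rule would then call for a test nearer the first dose. In 2.4 that rule covers woman 2. In 8.2 it carries the same limit and does not.

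**Other safeguards.** Sections 2.4 and 8.2 exclude pregnant women, but pregnancy is not among the 12 items in section 5.2. Withdrawal item 2 in section 7.2 needs a positive test. Section 8.3.9 acts once a participant reports pregnancy. The pre-procedure evaluation and weekly calls in 8.2 specify no pregnancy test. These narrow the risk, but for an unrecognised pregnancy only the 2.4 test requirement closes it.

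**The case against.** The strongest reply is that 2.4 already gives the right rule. It requires a pre-drug test of any pre-menopausal woman without hysterectomy and does not borrow the 8.2 definition. A site must follow the whole protocol, so skipping the test would breach 2.4. This stands. A reader might infer from 8.2 that the protocol waives pregnancy testing for recently amenorrhoeic women. The documents do not support that, because the waiver appears only when 8.2 is applied alone.

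A reader might also infer that contraception is waived for her. That goes too far as well: inclusion criterion 6 imposes it separately, although on a group it does not define.

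A second reply is that menses having ceased, placed beside hysterectomy, may mean menopause. On that reading woman 2 is not exempted and the unsafe conflict disappears. This is a fair alternative, but the sentence does not mention menopause, whereas 2.4 expressly uses menopausal status. Even so read, the sentence would exempt recently menopausal women and pass over those long past menopause, so the interval is wrong either way.

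A third reply is that staff would probably recognise the slip, and that the consent form and site forms may carry correct wording. Those forms are not available here, so this can be neither confirmed nor ruled out.

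**Conclusion.** The 8.2 time condition is reversed, and the section contradicts 2.4 for a pre-menopausal woman with recent amenorrhoea. The documents do not say which definition governs. The drop from two scheduled tests to none for that woman is a worst case. It assumes that a site applies 8.2 alone and reads ceased menses to include recent amenorrhoea. The documents give no figures on participants' sex or menstrual status, so no head-count can be offered.

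Power, alpha and the primary endpoint are unaffected. The point should still be fixed, because the term decides who is tested before study drug and before a research endoscopy, and the correction costs very little.

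**What to change.** Either of two changes removes the error.

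1. Reword the 8.2 sentence so that a woman is not of child-bearing potential if she is post-menopausal with menses ceased for more than 2 years, or after hysterectomy. The clinical investigators should confirm the interval.
2. Delete the 8.2 sentence and rely on the 2.4 definition.

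In either case, use the one definition in the Schedule of Activities footnote, section 2.4, section 5.1 item 6, section 7.2 item 2 and section 8.2.

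The cost is one sentence and matching wording in the other places, with no new type of procedure. The first option has one small consequence. A woman 18 months past menopause, whom neither current definition requires to be tested, would have the two tests already in the schedule, and 2.4 would have to be aligned. That is a clinical choice that correcting the error does not force, since the second option avoids it.
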